1. Calculate the 10 years incidence of total CVD, all-cause mortality and each major DM complication in Chinese DM patients in primary care.
2. Determine the risk factors that significantly predict total CVD, all-cause mortality and each major DM complication for Chinese DM patients in primary care.
3. Develop and validate risk prediction models for total CVD, all-cause mortality and each major DM complication for Chinese DM patients in primary care.
4. Develop a risk prediction nomogram and chart for the risk of total CVD, all-cause mortality for Chinese DM patients in primary care

Hypotheses

The following hypotheses will be tested:

1. Patient socio-demographic, clinical parameters, disease characteristics, and treatment modalities (these independent variables are described in the Methods section) are predictive of 10-year risk of total CVD, all-cause mortality and individual DM complication as a dependent variable.
2. The risk prediction models for total CVD, all-cause mortality and individual DM complication developed in this study can have over 70% of discriminating power.

d) **Plan of Investigation:**

(i) **Study design**

A 10-year retrospective study on a population-based cohort of Chinese DM patients in primary care.

(ii) **Subjects**

The cohort will include all patients with a documented clinical diagnosis of DM and were receiving care in the Hospital Authority (HA) primary care General Out-Patient Clinics (GOPC) and Family Medicine Clinics (FMC) on or before 1 July 2006 identified from the HA clinical management system (CMS) database.

Inclusion criteria

1. Age \geq 18 years old
2. At least 1 GOPC/FMC attendance on or within 1 year before 1 July 2006
3. Had a CMS record of the coding of ICPC-2 of T89 (Diabetes insulin dependent) or T90 (Diabetes non-insulin dependent) on or before 1 July 2006

Exclusion criteria

1. Patients who had a diagnosis of any DM complications defined by the relevant ICPC-2 or ICD-9-CM (shown in the Method section) on or before 1 July 2006.
2. Patients exclusively managed by Specialist Out-Patient Clinic (SOPC) on or before 1 July 2006.

Sample size calculation

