The detailed sample size calculation for each study outcome is attached in Appendix B. The required sample size is based on the requirements for the development and validation of the least common DM complication of ESRD. Specifically, based on our previous study, the 5-year incidence of ESRD was 1.9%(8), which can be extrapolated to a 10-year incidence of ESRD was 3.8% by assuming a constant incidence rate over time. To develop the risk prediction model for ESRD by multivariable Cox proportional hazard regressions with forward stepwise variables selection on 16 potential risks factors, we need 21,053 subjects using the 1 in 50 rule that 1 candidate predictor can be studied for every 50 events (23). To validate the risk prediction models, the area under the receiver operating characteristic curve (AUC) will be used to assess the discriminatory power of the predictive model on a separate sample of subjects. With 10 years incidence rate of ESRD was 3.8%(8), a total 14,307 subjects (544 subjects with ESRD and 13,763 subjects without ESRD) is needed to

ensure a precision of 0.05 for AUC of 0.7 by a 95% confidence interval.

Hence, a total 35,360 male and 35,360 female are needed for the development (training dataset) and validation of risk prediction models stratified by gender. The HA data set that we have obtained for our 5-year evaluation of quality of care and effectiveness of RAMP-DM study(8) has identified 120,857 DM patients under the care of public primary care on or before 1 Jan 2009, so we should be able to obtain sufficient number of subjects.

(iii) **Methods**

Each patient will be followed from 1 July 2006 to 31 December 2016 for the development of the indicator DM complications and mortality.

Definition of indicator DM complications

The incidence of four major DM complications (CHD, stroke, heart failure and ESRD), total CVD and all-cause mortality will be calculated. The incidence is counted from the earliest date of documented diagnosis defined by the relevant ICPC-2 and/ or ICD-9-CM coding recorded in the HA CMS database from 1 July 2006 to 31 December 2016. The relevant ICPC-2 and ICD-9-CM codes of each DM complication and mortality are determined by the academic and HA clinician co-investigators as listed below:-

1. CHD (ischaemic heart disease, myocardial infarction (MI), coronary death or sudden death) is defined by any of ICPC-2 K74 to K76 and ICD-9-CM 410.x, 411.x to 414.x, 798.x

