Cox proportional hazard regressions with forward stepwise method will be used to develop the risk prediction models for total CVD, all-cause mortality and each of 4 major DM complications. If the main term of a clinical parameter is selected in the models, the quadratic term of such clinical parameter will be evaluated. Afterwards, the interaction terms between selected predictors and age will be also examined in the risk prediction models. Cox regressions is the most commonly used method in risk prediction models in the Framingham Heart Study (9, 10) and UKPDS (11, 12). It allows us to estimate the risk of disease or death for an individual, given their prognostic variables. A positive hazard ratio means a higher likelihood of event associated with that specific variable. Conversely, a negative hazard ratio means a lower likelihood of the event associated with that specific variable. The key proportional hazards assumption will be assessed by examining plots of the scaled Schoenfeld residuals against time for the covariates. Any non-random pattern indicates a violation of the proportional hazards assumptions in which case transformation of covariates may be considered. For example, all continuous variables were naturally logarithmically transformed to minimize the influence of extreme values and to

improve discrimination and calibration of the models. A parametric approach such as exponential or Weibull distribution for the hazard function can also be carried out. A total of 6 risk prediction models will be established for total CVD, all-cause mortality and each of 4 major DM complications. The log of the hazard ratio of each selected risk factor in the final model will be used as coefficient weights in the prediction model of each relevant outcome. The risk equations for 10 year's follow-up will be established by combining these weights with the survivor function(9). A receiver operating characteristic (ROC) curve of predicted risk against observed events will be used to determine the risk threshold for the predicted outcomes as the risk threshold with the highest sum of sensitivity and specificity of the actual observed events.

Validation of risk prediction models

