In order to enable the 10-year risk prediction models for total CVD and all-cause mortality to be applied in busy clinical setting, risk prediction nomograms and charts will be developed for men and women. For the nomogram, the patient's score for each predictor is plotted on the appropriate scale and vertical lines are drawn to the line of points to obtain the corresponding scores. The score of each predictor will be transformed based on the estimated standardized beta coefficient of each predictor from the risk prediction model. For the continuous predictors (e.g. age), the line with interval depends on it units from minimum to maximum values among studies subjects (e.g. 20, 40, 60, 80 years old) will be displayed on the nomogram plot and the corresponding scores will be obtained based on the estimated standardized beta coefficient of the predictor (e.g. assign age of 20 to 0 point, age of 40 to 2 points, age of 60 to 4 points, age of 80 to 6 points). For categorical predictor (e.g. gender), each level of the predictor will be ranked a corresponding score based on the estimated standardized beta coefficient of the predictor (e.g. assign female to 0 point, male to 3 points). We have developed a similar nomogram on the risk of DM in a previous study as shown in Appendix C (24). All scores are summed to obtain a total score. The total score is plotted on the total line with corresponding predicted risk of CVD. Moreover, we will develop risk prediction charts similar to those developed by the Joint British Society as shown in Appendix D. The most significant predictors, up to a maximum of five, found in the full Cox regression models will be selected to classify subjects into 10-year CVD risk groups of <10% (low risk), 10%-20% (medium risk) and >20% (high risk). The Kaplan-Meier survival curves of each risk group will be developed and compared by log-rank tests to confirm the hazard ratios are significantly different among all risk groups.

STATA software version 13 (STATA Corp, College Station, Texas) will be used for data analyses. 5% is used as the level of significance in all statistical tests.

Strategies against anticipated problems

1. Missing data of risk factors

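### The list of significant risk factors (Objective 2) rests on forward stepwise selection alone, so it is unreliable for weak, null and closely correlated candidates

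*Combined protocol and SAP*

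**What the plan says.** The Aims section sets an inferential objective beside the prediction ones. Objective 2 is to "Determine the risk factors that significantly predict total CVD, all-cause mortality and each major DM complication". Hypothesis 1, that several families of patient factors predict 10-year risk, stands under the line "The following hypotheses will be tested". Outcome measure 2 in the Methods lists predictive factors separately from the models, which are outcome measure 3.

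The only adjusted analysis is in section (d)(iv), Development of risk prediction models: "Cox proportional hazard regressions with forward stepwise method will be used to develop the risk prediction models". The sample size section describes the same method for ESRD: "multivariable Cox proportional hazard regressions with forward stepwise variables selection on 16 potential risks factors". Quadratic terms and age interactions are then looked at for predictors already selected. Men and women are analysed separately, so six outcomes give twelve selections.

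The plan gives no entry level for the stepwise procedure. The nearest statement, at the end of (d)(iv), is that "5% is used as the level of significance in all statistical tests", and I take the entry level from it. The risk charts then use up to five predictors, chosen by significance.

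**The concern.** A predictor that appears in the final model is there because its p-value was small in the same data. Its reported p-value and HR are therefore conditional on having passed, and they behave differently from those of a factor fixed in advance. Weak factors that pass look stronger than they are, and null factors that pass look real. Among closely related candidates (systolic and diastolic pressure; the four lipid measures), chance partly decides which one enters.

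Objective 2 is the part at stake. The plan describes most of the factors as modifiable and relevant to practice, so a reader may act on the published list. The one-third hold-out sample and the bootstrap of the AUC check prediction performance. They do not check the p-values, the HRs or the membership of the list.

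**Working it through.** **The plan's own figure.** The inputs, all from the sample size section, are 16 candidates, the rule that "1 candidate predictor can be studied for every 50 events", and a 10-year ESRD incidence "extrapolated to a 10-year incidence of ESRD was 3.8% by assuming a constant incidence rate over time".

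16 × 50 / 0.038 = 21,052.6, which rounds up to the stated number: "we need 21,053 subjects using the 1 in 50 rule". This is 21,053 × 0.038 ≈ 800 ESRD events per sex, or 50 per candidate. A full main-effects model is therefore affordable even for the rarest outcome. Lack of events does not force selection.

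**A single weak factor.** Assumptions that are not in the documents: the true HRs, a standardised predictor uncorrelated with the others, and entry at two-sided 5%. With D events, SE ≈ 1/√D and Z has mean m = √D × ln(HR). The factor is selected if |Z| > 1.96. The HR reported after selection is exp(E[Z | selected] × SE). Coverage after selection is P(selected and |Z − m| < 1.96) / P(selected).

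For HR 1.05 at D = 800: SE = 0.0354 and m = 28.28 × 0.0488 = 1.38. P(selected) = 0.281, E[Z | selected] = 2.57, and the reported HR is exp(2.57 × 0.0354) ≈ 1.10. Coverage is 0.256 / 0.281 = 0.91.

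For a larger cohort, take all 120,857 patients that the plan mentions, split evenly by sex, with two-thirds used for development: 120,857 / 2 × 2/3 × 0.038 ≈ 1,531 events.

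| True HR per SD | Events | Selected | Mean HR when selected | Coverage when selected |
|---|---|---|---|---|
| 1.03 | 800 | 13% | 1.09 | 79% |
| 1.05 | 800 | 28% | 1.10 | 91% |
| 1.10 | 800 | 77% | 1.12 | 97% |
| 1.20 | 800 | over 99% | 1.20 | 95% |
| 1.03 | 1,531 | 21% | 1.07 | 88% |
| 1.05 | 1,531 | 48% | 1.07 | 95% |

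A null factor that is selected has zero coverage by construction.

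**The forward procedure itself.** I simulated 16 candidates at 800 events, eight with assumed HRs from 1.05 to 1.8 and eight null, with pairwise correlation 0 or 0.3. A factor with HR 1.05 was selected in 26–28% of runs, reported at 1.10–1.11, and covered in 84–91%. Factors with HR 1.2 or more were covered in 92–96%. At least one null entered in 32–35% of runs, against 1 − 0.95^8 = 34% for independent tests. At 2,000 events that chance was still 33–35%.

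**A correlated pair.** Take two predictors with assumed correlation 0.6 and true HR 1.10 each, at 800 events. Forward selection kept only one in about 76% of runs, each equally often, and both in about 24%. The survivor was reported at about 1.17. Most of that is the partner's effect being absorbed: alone in the model, its expected HR is 1.10^(1 + 0.6) ≈ 1.165. A joint test has noncentrality 800 × 2 × (ln 1.10)² × 1.6 ≈ 23.3 on 2 degrees of freedom, which gives power of about 99%.

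**What a full model gives.** With all 16 candidates fixed in advance at 800 events, coverage was 94.6–95.3% for every factor and HR 1.05 was estimated at 1.05. With eight nulls, the chance of at least one false factor at 5% was still 34%. At the Bonferroni level 0.05/16 = 0.0031 it was about 2.5%.

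**The case against.** The study is mainly about prediction. Its title, stated aim and Objectives 3 and 4 concern risk equations, and those are checked on a separate sample by discrimination, calibration and Brier score. Stepwise p-values do not affect that check. The candidates were chosen because the literature already linked them to complications, so a scenario with many nulls is pessimistic. Hypothesis 1 is about families of factors rather than single coefficients. My illustration uses the rarest outcome at the minimum sample, and commoner outcomes will have more events. All of this stands, and it limits the point to Objective 2, Hypothesis 1 and outcome measure 2.

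Stronger readings are tempting, but the documents do not support them:

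- A reader might infer that the plan's confidence intervals are invalid. It promises intervals for incidence and for the hold-out AUC, and selection spoils neither. It promises none for HRs, so the coverage figures above describe what would follow if such intervals were reported.
- A reader might infer that omitted factors will be declared non-predictive. The plan does not say so; the risk is that the list is read that way.
- A reader might count every possible quadratic and age interaction in all twelve models and forecast many false terms. Only terms for selected predictors are examined, and no term-by-term 5% test is spelled out, so that count is a ceiling the plan would not reach.
- The chart section speaks of full Cox models, which could be taken as an all-candidate fit. The wording is ambiguous, and no such fit is described.

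The unadjusted t-tests and chi-square tests do not fill the gap, because they ignore confounding and censoring.

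**Conclusion.** The concern holds for Objective 2, Hypothesis 1 and outcome measure 2. The plan asks which factors are significant and offers only a selected model to answer, so the list cannot be relied on for weak, null or closely correlated candidates. Exaggeration of weak effects is modest and shrinks as events accumulate. False entry of null factors does not shrink, and for correlated pairs the choice of survivor is largely arbitrary at 800 events. Strong isolated predictors are barely touched, and the prediction aim survives.

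The sizes depend on assumed HRs, an assumed correlation and an entry level inferred from the blanket 5% statement. The figure of 1,531 events is an upper case, since it uses every patient in a data set identified by 2009. The point is worth correcting before analysis, but it does not undermine the study.

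**What to change.** For Objective 2 and Hypothesis 1, add to (d)(iv) one pre-specified main-effects Cox model per outcome and sex containing all listed candidates. Report every HR with its 95% CI. Test related groups jointly (the four lipids; systolic with diastolic pressure). State a multiplicity adjustment, and whether it applies within each model or across all twelve, before any list of factors is called significant. The full model alone is not enough, because at 5% it carries about the same 34% chance of a false factor with eight nulls.

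Keep forward selection only to shorten the prediction equations, and state its entry level. Do not present its p-values as tests, and say that omission from an equation does not mean a factor has no predictive value.

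The cost is one extra fit per outcome and sex, longer tables, and some SAP wording; no new data are needed. Individual estimates for correlated factors will be imprecise: in the pair above, each factor's own 5% test has m = √(800 × 0.64) × ln 1.10 ≈ 2.16, hence power of about 58%. The adjustment also costs power for weak factors. For HR 1.10 per SD at 800 events, power falls from 64–77% at 5% to 26–40% at 0.0031. For HR 1.20 it stays at 93–99%. (Both ranges cover pairwise correlations from 0.3 down to 0.)

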We have also identified some deficiencies in existing risk prediction models that might have affected their accuracy. Firstly, gender is a factor that is of concern in the analyses of risk factors and CVD/mortality because males are typically associated with a higher risk of CVD/mortality (18), but statistical adjustment for gender is often insufficient to control for varying risk-factor profiles and CVD/mortality incidence (19). Secondly, there are possible interaction effects between age and risk factors on the CVD/mortality as the magnitude of the effect of specific risk factors such as LDL-C on the CVD/mortality may decrease with age (20). Thus, the interaction term between age and risk factors should be considered when developing the risk prediction models. Thirdly, many studies including our study and post-hoc analysis of JADE illustrated that there were curvilinear association (J or U shape) between HbA1c/ SBP/ DBP/ LDL-C/ BMI and the risk of CVD/mortality (21, 22), and thus the quadratic term of such clinical parameters should be evaluated when developing the risk prediction models. Finally, current risk prediction models were based on a single measurement (i.e. baseline) of clinical parameters such as HbA1c, SBP, DBP and BMI, but the use of repeated measures, e.g. average of all available readings or last available before event, may be more better predictors. The studies from JADE also suggest the inclusion of factors such as drug treatments and subsequent HbA1c and BP may improve the predictive power of the models (13, 14).

Inaccurate risk stratification may lead to inappropriate risk-stratified interventions. There is a need for new robust risk prediction models for the prediction of 10-year CVD risk and mortality for primary care Chinese patients to enable accurate risk stratification of DM patients in the HA on-going RAMP-DM or other primary care systematic risk-stratified multi-disciplinary management programmes. Furthermore,

robust risk prediction models for the overall prediction of first CVD and all-cause mortality can inform policy makers in service planning and resource allocation.

c) **Aims, Objectives and Hypotheses**

This study aims to develop 10-year risk prediction models for total CVD and all-cause mortality among Chinese diabetic patients in primary care. Risk prediction models for individual DM complications including CHD, heart failure, stroke and ESRD will also be developed.

The objectives are to:

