2. Stoke (fatal and non-fatal stroke) is defined by any of ICPC-2 K89 to K91 or ICD-9-CM 430.x to 438.x.
3. Heart failure is defined by any of ICPC-2 K77 or ICD-9-CM 428.x
4. CVD is defined as the presence of any of CHD, heart failure and stroke ICPC-2 or ICD-9-CM codes listed in 1, 2 and 3 above.
5. ESRD is defined by any of ICD-9-CM 250.3x, 585.x, 586.x, or an eGFR<15mL/min/1.73m².
6. Mortality is identified from the Hong Kong Death Registry.

Risk factors to be Included in the Risk Prediction Models

Risk factors (independent variables) previously found to be associated with DM

complications from the literature (4) and those that are routinely available in primary care are selected to strike a balance between comprehensiveness and feasibility. The potential risk factors that will be explored include those related to patient's socio-demographics, clinical parameters, disease characteristics and treatment modalities. Patient socio-demographics include sex, age and smoking status. Clinical parameters include body mass index (BMI), haemoglobin A1c (HbA1c), systolic and diastolic blood pressure, lipid profile (total cholesterol, HDL-C, LDL-C, triglyceride), estimated glomerular filtration rate (eGFR) and albuminuria. Disease characteristics include the duration of DM and co-morbidity. Treatment modalities include the use of specific anti-hypertensive drugs, insulin, specific oral anti-diabetic drugs and lipid-lowering agents. The operational definitions of the risk factors are shown in appendix A. These factors, except sex, age, duration of DM and co-morbidity, are modifiable, which have implications for practice.

Data collection

In the middle of 2017, anonymous data from 1 January 2006 to 31 December 2016 of all DM patients who satisfy the inclusion criteria and without any exclusion criteria will be extracted by the HA statistics team from the HA clinical management system (CMS) database. We have successful experience in working with the HA in the extraction of similar data from 2009 to 2013 for our extended evaluation on quality of care and effectiveness of RAMP-DM study (7), and we have obtained preliminary agreement from the HA for the data extraction in the present study.

Outcome Measures

1. The incidence of total CVD, all-cause mortality and each of 4 major DM complications over 10 years
2. Factors predictive of total CVD, all-cause mortality and each of 4 major DM complications over 10 years

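### Age and diabetes duration get no pre-specified non-linear term or linearity check, although selected predictors are then tested for interaction with age

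*Combined protocol and SAP*

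**What the plan says.** Section d)(iv), Development of risk prediction models, sets the order of model building. Predictors enter a Cox model by forward stepwise selection. Then comes the only planned look at non-linearity: "If the main term of a clinical parameter is selected in the models, the quadratic term of such clinical parameter will be evaluated". The next step is this: "Afterwards, the interaction terms between selected predictors and age will be also examined in the risk prediction models".

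Section d)(iii), on the risk factors to be included, uses clinical parameters as a named category: "Clinical parameters include body mass index (BMI), haemoglobin A1c (HbA1c), systolic and diastolic blood pressure, lipid profile", followed by eGFR and albuminuria. Age and duration fall elsewhere: "Patient socio-demographics include sex, age and smoking status" and "Disease characteristics include the duration of DM and co-morbidity". The Introduction's case for quadratic terms rests on J- or U-shaped associations for HbA1c, systolic and diastolic pressure, LDL-C and BMI, and concludes "thus the quadratic term of such clinical parameters should be evaluated when developing the risk prediction models". It names neither age nor duration.

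One other sentence bears on shape. After describing Schoenfeld residual plots, d)(iv) says: "Any non-random pattern indicates a violation of the proportional hazards assumptions in which case transformation of covariates may be considered". Its example is a natural-log transformation of every continuous variable, partly to improve discrimination and calibration.

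**The concern.** Age enters every interaction test, yet nothing in the plan checks its own shape first. Suppose the log hazard is curved in age but age is entered as a straight line. The product of age with a predictor that is correlated with age then partly stands in for the missing age-squared term, and it can be selected as an interaction when none exists. The misfit itself falls mainly where the age distribution is thin.

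The cohort takes all adults from 18, so the tails are within the models' scope. At stake are the absolute 10-year risks for younger patients, the equations and charts built from them, and objective 2, which reports the factors that predict each outcome.

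**Working it through.** **The plan's own figures.** The documents give no figure on the shape of age, so the relevant one is the development sample in d)(ii): 16 candidates × 50 events / 0.038 = 21,052.6, rounded up to 21,053 per sex. This matches the plan and is the sample size used in the first set of simulations.

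**Reading the passages together.** The quadratic step covers clinical parameters. Age is socio-demographic and duration is a disease characteristic. The step therefore reaches neither, and no spline, fractional polynomial or linearity check is planned for them elsewhere. The age scoring used to illustrate the nomogram (two points for every 20 years) is itself linear.

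**Simulation 1.** From the plan: n = 21,053, 5% significance, and 10-year incidence of 3.8% (ESRD). Assumed: an alternative incidence of 20%; age with mean 63 and SD 12, truncated to 18–95; three covariates correlated -0.5, 0.3 and 0 with age; no true interactions. With Z = (age - 63)/12, the log hazard is 0.7Z + qZ² plus linear covariate effects of -0.3, 0.2 and 0.2. The slope in Z is 0.7 + 2qZ. From age 45 (Z = -1.5) to 81 (Z = 1.5), it falls from 0.85 to 0.55 at q = -0.05, falls from 1.0 to 0.4 at q = -0.1, and rises from 0.4 to 1.0 at q = +0.1. Following the plan's order, each covariate's quadratic term was kept if p < 0.05, then its product with age was tested at 5%. There were 60 replicates per scenario, so a true 5% rate has a Monte Carlo standard error of √(0.05 × 0.95/60) = 2.8 percentage points.

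Results with age entered as linear:

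| q | Incidence | Predicted/true, under 45 | 45–80 | Over 80 | False interaction, r = -0.5 | r = 0.3 | r = 0 |
|---|---|---|---|---|---|---|---|
| 0 | 3.8% | 0.99 | 0.99 | 1.00 | 2% | 5% | 8% |
| 0 | 20% | 0.99 | 1.00 | 1.00 | 7% | 0% | 8% |
| -0.05 | 3.8% | 1.28 | 0.98 | 1.05 | 15% | 8% | 7% |
| -0.05 | 20% | 1.28 | 0.99 | 1.03 | 48% | 22% | 5% |
| -0.1 | 3.8% | 1.70 | 0.97 | 1.07 | 32% | 10% | 7% |
| -0.1 | 20% | 1.61 | 0.98 | 1.06 | 97% | 58% | 2% |
| -0.2 | 3.8% | 2.62 | 0.94 | 1.20 | 77% | 42% | 5% |
| -0.2 | 20% | 2.50 | 0.95 | 1.16 | 100% | 98% | 5% |
| +0.1 | 3.8% | 0.56 | 1.04 | 0.95 | 48% | 23% | 3% |
| +0.1 | 20% | 0.60 | 1.03 | 0.97 | 95% | 60% | 3% |

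With age squared added, the under-45 ratio was 0.98–1.03 and the false-interaction rate 0–10% in every scenario.

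With log(age) instead, the under-45 ratio was 0.88–0.90 at q = -0.05. It was 0.67–0.69 when age was truly linear, with false interactions up to 72%, and 0.35–0.40 at q = +0.1.

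**Simulation 2, true effect in log(age).** All inputs are assumed: 23,000 per sex, mean age 62 and SD 12, eGFR correlated -0.6 with age, 10-year risk 20–25%, and hazard rising 5, 6 or 8% per year at age 60. Linear age gave under-45 ratios of 1.30, 1.40 and about 1.6, and false age-by-eGFR interactions in 68, 80 and 98% of runs. Age squared brought the ratio to 1.05–1.08. In a re-run at 22% overall risk, log(age) gave 1.00. Mean risk under 45 in that re-run was 4.8% true against 6.2% predicted, 3.6% against 5.0%, and 2.0% against 3.2%: errors of 1.4, 1.4 and 1.2 percentage points. A separate accelerating scenario gave a ratio of 0.50, but its degree of curvature is not specified, so 0.56–0.60 is the firmer convex figure.

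**The case against.** A reader might infer that the plan forces age and duration to be log-linear. It does not: the log transformation it mentions would cover both, and it is exactly right if the truth is log(age). What stands against relying on it is that it is optional, is prompted by a pattern over time rather than by curvature in the covariate, and offers one fixed shape that does harm if the effect is linear or accelerating.

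A reader might also infer that any curvature produces false age interactions. It does not. The predictor must be correlated with age, and there must be enough curvature and events; the uncorrelated predictor stayed near 5%.

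The absolute errors can be small. In the log-age runs about 8% of the assumed cohort was under 45, at most 1.1% of them changed risk group at the 10% and 20% chart cut-offs, and 3.5–4.4% of all subjects did. Over 80, predictions were about 2 points too high on true risks of 51–66%. This stands, and it limits the harm to the charts in that scenario.

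Planned validation could reveal part of the problem, because young patients concentrate in the lowest predicted-risk group. A ten-group Hosmer-Lemeshow-type test in 11,500 validation subjects rejected in 28–55% of log-age runs and in 95% at q = +0.1. Detection is therefore incomplete. It also comes after the model is built, with no stated repair step and no check by age band.

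For duration, no size has been estimated. Its operational definition is in Appendix A, which is not available here. If duration is categorised there, the point does not apply to it.

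**Conclusion.** The gap stands on the text: no non-linear term or linearity check is pre-specified for age or diabetes duration, while selected predictors are tested for interaction with age. The consequence is conditional. If the log hazard is linear in age, the planned form is adequate and nothing is lost; the documents do not show which case holds.

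If the slope falls roughly 1.5- to 2.5-fold between ages 45 and 81, risk under 45 is over-predicted by about 30–70%, which is 1.2–1.4 percentage points in the log-age scenario. If the slope rises 2.5-fold, risk under 45 is under-predicted by about 40–44%. Average risk at ages 45–80 stays within about 7% throughout. False interactions depend on the number of events: for a predictor correlated -0.5 with age and q = -0.1, 32% at the ESRD incidence against 97% at 20%. Milder curvature (q = -0.05) gives 15% and 48%. All of these rest on the assumed age distribution, correlations and effect sizes. The point is worth settling before analysis because the remedy is small, but it does not show that the models will be wrong.

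**What to change.** In d)(iv), Development of risk prediction models, extend the non-linearity step to age, and to diabetes duration if it is entered as continuous, using a quadratic term or a restricted cubic spline. Do this before the age-interaction step, and keep the selected age terms in the model while interactions are tested. In the validation section, add observed against predicted risk by age band.

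The cost is a few sentences and up to two more candidate terms per model if quadratics are used. The plan does not say whether its 16 candidates already include quadratic and interaction terms. If the two count under the 1-in-50 rule, ESRD development needs 18 × 50 / 0.038 = 23,685 per sex instead of 21,053. Splitting the plan's minimum of 35,360 per sex 2:1 already gives 23,573 for development, 112 short. The 120,857 patients cited in d)(ii) would give about 80,571 for development (two-thirds) against 2 × 23,685 = 47,370. This looks feasible, although that count is for 2009 and its split by sex is not given.
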